9.2 Subject demographics and other baseline characteristics

All data for background and demographic variables will be listed by treatment group and subject. Summary statistics will be provided by treatment group.

Subject demographics will include age, sex, race, ethnicity, height, weight and BMI. Other baseline disease characteristics include relevant medical history, current medical conditions, results of laboratory screens, transplant history, donor characteristics (e.g., age, sex, race, type, CIT) and any other relevant information.

Summary statistics will be presented for the subjects in the Full Analysis Set.
Corporate Confidential Information

Categorical data will be displayed via absolute and relative frequencies for each category (including a category labeled as “missing” when appropriate).

9.3 Treatments (study drug, rescue medication, other concomitant therapies, compliance)

Data for study drug administration (rescue medication) and concomitant therapies will be listed by treatment group and subject.

9.3.1 Study medication

The duration (days) of study medication administration will be summarized. This will be calculated by subtracting the date of the last administration of study medication from the date of first administration and then adding the dosing interval for CFZ533 or Tac (i.e., 28 days for treatment administered once every 4 weeks). In calculating the duration of treatment, days of temporary interruption of study medication for any reason will be included. Further, the frequency of dose changes (including temporary dose interruption) will be presented by reason for the change.

Average daily doses will be presented by treatment. “Zero” will be used for periods of temporary interruption of study medication for any reason.

The number and percentage of subjects who prematurely discontinued study medication will be summarized by reason for discontinuation.

9.3.2 Concomitant immunosuppressants

The average daily dose of administered MMF, Tac and CS will be summarized by treatment arm for subjects on study medication. The dose of the induction agent will be summarized for each of days when it was administered.

The dose of antibodies used for the treatment of acute rejection episodes will be recorded as well.

9.3.3 Other co-medications

Concomitant medications, other than immunosuppressants and CS mentioned above, will be summarized by therapeutic class and preferred term by presenting the number and percentage of subjects using each medication for each treatment group.

9.4 Analysis of the primary variable(s)

9.4.1 Variable(s)

Parts 1 and 2:

The primary variable is tBPAR after 3 months of treatment. For the analysis in Part 2, the total “on treatment time” in each treatment group is required.

Corporate Confidential
Information

Corporate Confidential Information

9.4.2 Statistical model, hypothesis, and method of analysis

Handling of missing values/censoring/discontinuations

The primary analysis only considers the events “on treatment” (apply the window defined in [Section 9.4.1](#)), thus accounting for discontinuations from the randomized treatment arm or study.

Part 1

The number of patients with tBPAR is assumed to follow a binomial distribution, i.e.,

$r_i \sim \text{Binomial}(n_i, \theta_i)$, where r_i is the number of patients with tBPAR in treatment group i, n_i is the number of patients in treatment group i and θ_i is the probability of tBPAR.

Corporate Confidential Information

The posterior mean tBPAR rate will be presented together with the 95% credible interval.

Part 2

The number of patients with tBPAR is assumed to follow a binomial distribution, i.e.,

$r_i \sim \text{Binomial}(n_i, \theta_i)$, where r_i is the number of patients with tBPAR in treatment group i, n_i is the number of patients in treatment group i and θ_i is the probability of tBPAR.

The primary efficacy analysis for the first 3 months of Part 2 evaluates whether a CFZ533 treatment arm meets the pre-defined success criteria

Corporate Confidential Information

$\Pr(\theta_{CFZ5331} - \theta_{SOC} < 0.20 \mid \text{data}) > 60\%$.

The required posterior probabilities will be estimated from simulations of the posterior distributions of $\theta_{CFZ533} - \theta_{SOC}$ and compared to the thresholds for the levels of proof.

The prior distributions will be assumed to be a non-informative Beta(1/3,1/3) for CFZ533 and an informative prior of Beta(1, 13) for placebo. This informative prior corresponds to an approximate mean response rate of 7% with a 95% confidence interval of (0.2%, 24%) and was determined via a meta-analysis of control therapies (see [Section 9.6](#)).

The posterior mean tBPAR rates for each treatment group and for the difference in mean response rates between treatments will be presented together with 95% credible intervals.

Corporate Confidential Information

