2.2 Study Part 2: CNI-free Proof-of-Concept

2.2.1 Primary objective

- To assess the potential for CFZ533 to act as the primary immunosuppressant in a CNI-free regimen with MMF in *de novo* renal transplant patients as assessed by tBPAR at Month 3 post-transplantation

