6.1.3 Statistical model, assumptions and hypotheses

The number of patients with tBPAR is assumed to follow a binomial distribution, i.e.,

$$r_i \sim \text{Binomial}(n_i, \theta_i)$$

where r_i is the number of patients with tBPAR in treatment group i , n_i is the number of patients in treatment group i and θ_i is the probability of tBPAR.

The efficacy analysis for the first 3 months of Part 2 considers whether a CFZ533 treatment arm meets the pre-defined criteria for initiation of Part 3.

The pre-defined success criteria is considered to be a tBPAR rate difference between the CFZ533 arm and the control group of less than 20 percentage points with at least 60% level of proof.

$$\Pr(\theta_{\text{CFZ533}} - \theta_{\text{SoC}} < 0.20 \mid \text{data}) > 60\%$$

The required posterior probabilities will be estimated from simulations of the posterior distributions of $\theta_{\text{CFZ533}} - \theta_{\text{SoC}}$ and compared to the thresholds for the levels of proof.

The prior distributions will be assumed to be a non-informative Beta(1/3, 1/3) for CFZ533 and an informative prior of Beta(1, 13) for SoC. This informative prior corresponds to an approximate mean response rate of 7% with a 95% confidence interval of (0.2%, 24%) and was determined via a meta-analysis of control therapies.

The posterior mean tBPAR rates for each treatment group and for the difference in mean response rates between treatments will be tabulated together with the 95% credible intervals, the number of patients with tBPAR and the posterior probabilities of being above the thresholds, 10%, 15%, 20%, 25%.

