6.1.4 Supportive analyses

Kaplan-Meier estimates

In this analysis, patients who have not experienced tBPAR, will be censored with the censoring time as defined by the last contact day at or before the cut-off point (e.g., 1st IA Month 3 visit, 2nd IA Month 6 visit). The patients will be considered as completed at the date of their corresponding analysis cut-off point. In addition to the Kaplan-Meier plot, a log-rank test shall be performed to obtain estimates with CI's for each treatment arm and the difference between treatment arms.

During data review, it was noticed that some patients were switched from the randomized treatment to another regimen. Therefore in future IA's, more focus shall be placed on the Kaplan-Meier analysis.

Supportive Bayesian analysis

In addition the Bayesian analysis will be repeated with a model using a Poisson distribution to account for the patients that may switch treatment or discontinue early from the study. The following parametrization will be used:

The number of tBPAR events in group i is assumed to follow a Poisson distribution, i.e.

$$y_i = \text{Poisson}(\mu_i),$$

where μ_i is the expected number of events in group i, with

$$\mu_i = \lambda_{i,T} * t_{i,T},$$

with $t_{i,T}$ being the total follow up time in group i (times censored at treatment switch or discontinuation) up to analysis time point T and λ_i being the event rate in group i up to the analysis time point T. For sensitivity analysis of the primary analysis the analysis time point T is week 12 (i.e. week 13 visit, month 3 after transplantation). The probability of an tBPAR event occurring up to the analysis time point can then derived as $\theta_i = 1 - \exp(-\lambda_i * T)$.

The pre-defined success criteria is considered to be a difference in the probability of tBPAR between the CFZ533 arm and the control group of less than 20 percentage points with at least 60% level of proof.

$$\Pr(\theta_{CFZ533} - \theta_{SoC} < 0.20 | \text{data}) > 60\%$$

The required posterior probabilities will be estimated from simulations of the posterior distributions of $\theta_{CFZ533} - \theta_{SoC}$ and compared to the thresholds for the levels of proof.

The prior distributions will be assumed to be a non-informative Beta(1/3,1/3) for θ_{CFZ533} and an informative prior of Beta(1, 13) for θ_{SoC} .

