Data for CFZ533 administration and concomitant therapies will be listed by treatment group and patient. The duration (days) of CFZ533 study medication administration will be summarized and listed. The duration will be calculated by subtracting the date of the last administration of study medication from the date of first administration and then adding the dosing interval for CFZ533. In calculating the duration of treatment, days of temporary interruption of study medication for any reason will be included, i.e, any days of interruptions will not be excluded from the duration of treatment. Further, the frequency of dose changes (including temporary dose interruption) will be presented by reason for the change.

Average daily doses of each treatment will be presented in a summary table and will be listed by treatment and patient. “Zero” will be used for periods of temporary interruption of study medication for any reason.

The number and percentage of patients who prematurely discontinued study medication will be summarized by reason for discontinuation.

If the number of events allow, Kaplan-Meier (KM) estimates of time to discontinuation of study medication curve will be constructed and presented graphically. In this analysis, patients

who have not discontinued study medication will be censored with the censoring time as defined by the last contact day.

Concomitant immunosuppressants

The dose of administered Basiliximab, MMF, Tac and CS will be listed by treatment and patient.

The dose of antibodies used for the treatment of acute rejection episodes will be summarized by treatment and listed by treatment and patient.

Other co-medications

Concomitant medications, other than immunosuppressants and CS mentioned above, will be listed by patient and summarized by therapeutic class and preferred term by presenting the number and percentage of patients using each medication for each treatment group.

Calculated eGFR

The main safety endpoint is calculated eGFR.

Patients will be considered as “on treatment”, whilst they are taking their assigned randomized treatment. If a patient switches to an alternative treatment or stops taking their assigned randomized treatment, this data will be excluded from the summaries, figures and analysis for eGFR data.

Calculated eGFR as determined by the central lab will be summarized by visit. The calculated eGFR will be presented graphically to show the overlaid patient profiles and mean profile over time.

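### The Month 3 go rule counts only on-treatment rejections over all patients, so leavers count as non-events, and Protocol and SAP do not agree on which rejections count

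*Protocol*

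**What the plan says.** The Part 2 objective (Protocol 2.2.1) is the potential of CFZ533 as primary immunosuppressant, "as assessed by tBPAR at Month 3 post-transplantation". Protocol 9.4.1 defines the primary variable over three months of treatment and says that for Part 2 the total on-treatment time "in each treatment group is required". The on-treatment window itself is redacted.

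Protocol 9.4.2 then admits only on-treatment events, "thus accounting for discontinuations from the randomized treatment arm or study". Its visible Part 2 model is Binomial(n_i, theta_i), with n_i the size of the group. The full analysis set (9.1) requires only a dose and a transplant.

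SAP 6.1.3 repeats the model, in which "n_i is the number of patients in treatment group i", with the same priors and the same criterion: Pr(difference < 0.20) > 60%. It states no on-treatment restriction. For eGFR, SAP 7.1.2 does state one: "If a patient switches to an alternative treatment or stops taking their assigned randomized treatment, this data will be excluded from the summaries".

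SAP 6.1.4 records that "it was noticed that some patients were switched from the randomized treatment to another regimen" and gives two supportive analyses. In the Kaplan-Meier analysis, "patients who have not experienced tBPAR, will be censored with the censoring time as defined by the last contact day". The Poisson model uses follow-up "times censored at treatment switch or discontinuation".

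**The concern.** Restricting the numerator while keeping the whole denominator does not adjust for discontinuation. It assumes that a patient who leaves without a counted rejection would have stayed free of rejection to Month 3. The on-treatment time that 9.4.1 calls for, which could correct this, does not appear in the visible primary model.

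The protocol provides several ways to leave without a rejection: BK nephropathy, persistent or severe over-immunosuppression, and anti-thymocyte globulin for delayed graft function (5.5.5), and confirmed tuberculosis (6.6.7). The over-immunosuppression switch is written for CFZ533, so unequal stopping is plausible.

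The documents also leave the primary numerator open. Under Protocol 9.4.2 a rejection after a switch, once outside the window, does not count. SAP 6.1.3, read literally, would count it. Two programmers could derive different values of r_i, and that count feeds the proof-of-concept decision.

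**Working it through.** **Inputs.** 30 and 15 patients (Protocol 3.1.4); priors Beta(1/3, 1/3) for CFZ533 and Beta(1, 13) for control; go if Pr(theta_CFZ533 − theta_SoC < 0.20 | data) > 0.60 (Protocol 9.4.2, SAP 6.1.3). With r and s events, the posteriors are Beta(1/3 + r, 1/3 + 30 − r) and Beta(1 + s, 13 + 15 − s). The probability is obtained by numerical integration.

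**1. Reproducing the plan's own cut-offs.**

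| Control events | Last go | First no-go |
|---|---|---|
| 0 | 6/30: 0.656 | 7/30: 0.495 |
| 1 | 7/30: 0.642 | 8/30: 0.496 |
| 2 | 8/30: 0.633 | 9/30: 0.498 |

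The first no-go counts 7, 8 and 9 equal the efficacy termination counts in Protocol Appendix 3. They arise with full denominators: dropping three leavers gives 6/27 against 0/15 = 0.547, already a no-go. This supports reading n_i as all patients. It also shows that one uncounted rejection reverses the result at each boundary.

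**2. Effect on the observed rate.** The documents give no discontinuation rate by Month 3, so d = 20% and 30% are assumptions. Take constant hazards over the three months (time scaled to 1), stopping independent of rejection, and no window after the last dose. Let lam = −ln(1 − p) and g = −ln(1 − d).

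On-treatment rate = lam/(lam + g) × [1 − exp(−(lam + g))].

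For p = 27%, lam = 0.3147.
- d = 20%: g = 0.2231; 0.3147/0.5378 × (1 − 0.584) = 24.3%.
- d = 30%: g = 0.3567; 0.3147/0.6714 × (1 − 0.511) = 22.9%.

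Counting all events adds the integral over 0 to 1 of g·exp(−(lam + g)t)·(1 − exp(−m(1 − t))), where m is the hazard after the switch. If leavers take a three-month risk of 7–10%, the all-event rate is 25.0–25.3% (d = 20%) or 23.9–24.4% (d = 30%). That is 0.20–0.29 or 0.31–0.44 extra events per 30 patients.

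**3. Chance of a go.** True rates 27% and 7%, before stopping rules, by enumeration of Binomial(30) × Binomial(15). With no discontinuation it is 42.4%.

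| Who leaves (20% / 30%) | On-treatment count | All events, leavers at 7–10% risk |
|---|---|---|
| CFZ533 only | 54.7% / 61.4% | 50.2–51.6% / 54.5–56.6% |
| Both arms equally | 53.1% / 59.1% | 50.9–51.6% / 55.6–56.6% |
| Control only | 40.7% / 39.8% | not calculated |

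With CFZ533-only leaving, the gap is 54.7 − 51.6 = 3.1 to 61.4 − 54.5 = 6.9 points. With equal leaving it is 53.1 − 51.6 = 1.5 to 59.1 − 55.6 = 3.5 points. If CFZ533 leavers keep the CFZ533 risk, counting all events returns 42.4%. Control-only leaving makes the criterion slightly harder to meet than 42.4%.

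**4. With a stopping rule applied to all tBPARs at N = 30, CFZ533-only leaving.**
- Stop at 9 of 30 (SAP Table 1-1): 52.0–52.5% on-treatment against 48.9–50.3% for d = 20%; 58.1–58.9% against 53.3–55.5% for d = 30%. The gap is about 2 to 5 points.
- Appendix 3: both counts give 48.9–50.3% and 53.3–55.5%. The gap is nil, because its termination counts coincide with the first no-go counts in step 1.

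The two rules themselves differ: 7 against 0 terminates the arm under Appendix 3 but not under Table 1-1, which needs 9 of 30.

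**5. The Poisson model.** If only first events count, follow-up continues after the event and no rejecting patient stops treatment, then 27% reads as 1 − exp(−0.27) = 23.7% and 7% as 1 − exp(−0.07) = 6.8%. A 20-point difference becomes 16.9.

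**The case against.** **Redaction.** Text is blacked out around the variable in 9.4.1 and the model in 9.4.2. A window after the last dose would narrow the gap, and hidden text may say how on-treatment time is used. This stands as a limit on the size. It does not remove the visible mismatch, and SAP 6.1.3, which shows no redaction, has the same patient-count binomial.

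**The SAP already covers it.** The Poisson analysis allows for switching with the same criterion, and the SAP promises more weight on Kaplan-Meier at later looks. The two can be read as complementary. Both are supportive, however, and the go rule stays binomial.

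**The SAP may already count everything.** Read literally, 6.1.3 does. It was also written from protocol version 02 and describes three parts, where the supplied protocol has two, so version drift may explain some of the difference. The documents still need to say which count is meant.

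**On-treatment is a legitimate question.** Both documents define the primary variable in terms of treatment, and the question suits a proof of concept. It then needs an exposure-based estimate, not a reduced numerator over a full denominator.

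**The effect is modest and the remedy partial.** This is fair. With CFZ533-only leaving, counting all events removes about a quarter to just over a third of the rise: (54.7 − 51.6)/(54.7 − 42.4) = 25% to (54.7 − 50.2)/12.3 = 37%. The remainder reflects leavers' lower assumed risk on other therapy, which is not a counting artefact.

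**Timing.** Switching had been noticed when the SAP was written and the trial is open-label, so a change to the numerator must be documented as made with that knowledge.

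**Conclusion.** The concern holds. The sentence in Protocol 9.4.2 is wrong as written: on-treatment counting over all patients treats leavers without a counted rejection as event-free to Month 3. Protocol and SAP do not settle the primary numerator between them.

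The criterion becomes easier to meet when leaving is equal or greater on CFZ533, and slightly harder when only control patients leave. The sizes in the working rest on assumed discontinuation of 20–30%, constant hazards, no post-dose window and a true difference at the 20-point margin. They shrink with less discontinuation, and the protection Appendix 3 could give depends on which tBPARs it counts, which is not stated. The point should be fixed because single patients decide the criterion.

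**What to change.** - In Protocol 9.4.2 and SAP 6.1.3, define r_i as the number of patients in the full analysis set with a tBPAR up to the Month 3 visit, by randomised arm, whether or not they switched or stopped. State this as an exception to the rule of analysing by treatment received (Protocol 9.1, SAP section 4).
- Leave the priors and the 0.20/60% criterion unchanged.
- Delete the claim that on-treatment counting accounts for discontinuations.
- Keep the on-treatment question as a supportive, exposure-based analysis. If the Poisson model counts first events only, end each patient's time at the earliest of tBPAR, switch or discontinuation.
- State which tBPARs Appendix 3 and SAP Table 1-1 count, and reconcile those two passages. No view is taken here on which stopping rule is right.

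**Cost.** Wording in two documents, plus a dated record that switching had already been seen. No new data are needed: Protocol 5.5.10 and section 6 ask patients who stop treatment to stay in the study to Month 12. The downside is that rejections on the switched-to regimen count against the assigned arm, so the CFZ533 estimate may look less favourable.

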9.4.3 Supportive analyses

Part 2

The tBPAR (or BPAR) rate will be analyzed at 6 months and 12 months post transplantation using the same method as described for the month 3 analysis in [Section 9.4.2](#).

9.5 Analysis of secondary and exploratory variables

9.5.1 Efficacy

Other efficacy variables will be analyzed similarly to the primary efficacy endpoint, although without the non-inferiority test:

- tBPAR at Months 3, 6 and 12
- BPAR at Months 3, 6 and 12
- Graft loss at Months 6 and 12
- Death at Months 6 and 12
- Graft loss or death at Months 6 and 12
- Antibody mediated tBPAR at Month 12

For each of the efficacy endpoints (primary and secondary), simple event rate estimates (proportion of events) will be obtained and each CFZ533 treatment arm event rate will be compared with the control arm event rates using Z-statistics based on two-sided 95% confidence intervals for differences in event rates.

As supportive analyses, BPAR and tBPAR will also be analyzed using the adjudicated results.

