Acute rejections should be treated with bolus methylprednisolone (other CS are acceptable at an equivalent dose) according to local practice. Recommended treatment is with at least 3 boluses of IV methylprednisolone with a minimal dose of 250 mg/bolus or at least 2 boluses of IV methylprednisolone with a minimal total dose of 750 mg.

Patients who experience steroid-resistant rejections, vascular rejections or rejections with a Banff grade \geq 2B ([Appendix 8](#)) should be discontinued from study treatment, converted to local SoC and may be treated with other anti-rejection therapies (i.e., antibody therapy).

All medications used for the treatment of suspected or confirmed acute rejections must be recorded on the Concomitant Medications eCRF under the Immunosuppressive category.

Management of signs of over-immunosuppression

CFZ533 was highly effective in preventing renal transplant rejection in NHP when used as monotherapy. Combining CFZ533 with MPA and CS after basiliximab induction may increase the risk for over-immunosuppression (e.g. BK viremia). For CFZ533 to be effective, full inhibition of CD40 signaling is required. Reducing the CFZ533 dose is not advisable, since under-dosing of CFZ533 may trigger loss of immunosuppression. In case of suspected over-immunosuppression clinical sites should first consider reducing the MPA level by 50 % or more (if MPA is completely stopped, CS may be slightly increased) with a follow up within the next weeks as per local practice. If there still are signs of over-immunosuppression, they should consider removing MPA and/ or reduce CS. If there still are signs of over-immunosuppression, or if the symptoms are severe, patient should be discontinued from CFZ533 and be switched to SoC.

Management of BK viremia

In case of diagnosed BK virus in urine, MPA levels should be reduced as a first measure as described in the Section above “Management of signs of over-immunosuppression”. Patients are considered to have significant BK viremia when their plasma PCR results report \geq 10,000 copies/mL of BK virus ([Sood et al 2012](#)).

If a patient is found to have BK viremia that reaches \geq 10,000 copies/mL in plasma, reducing/ stopping of MPA should be considered as a first measure. If patients have biopsy-proven BK nephropathy they should be discontinued from their randomized treatment and be switched to standard-of-care treatment as per local center practice.

Management of Patients with Delayed Graft Function (DGF)

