DGF for this trial is defined as:

- A dialysis performed within 7 days of transplant
- ***excluding*** up to two dialysis sessions to correct electrolyte abnormalities (e.g., hyperkalemia) in the post-transplant time period

In case a patient experiences DGF, the DGF is by definition starting at reperfusion after the transplantation procedure. If the graft dysfunction is starting later according to the Investigator, then this condition is considered secondary graft dysfunction.

DGF must be reported as an AE for patients who experience DGF without requiring dialysis. In case DGF is reported as an AE and dialysis is also reported, the end of DGF is considered the day the last dialysis session ends.

In case of DGF, treatment will be according to local practice. DGF treatments must maintain

sufficient immunological coverage for the graft and may include maintaining, interrupting or reducing the dose of study drug and the use of anti-thymocyte globulin. If a polyclonal antibody or anti-thymocyte globulin is used, the study treatment must be discontinued and the subject will be placed on standard of care per local practice.

Primary graft non-function (PGNF) is defined as dialysis started 7 days after transplantation with a continuous record of post-transplant dialysis until either transplantectomy or death. PGNF should be reported on the Graft Loss eCRF.

If a subject is placed on permanent dialysis (or retransplanted), study treatment must be discontinued, the Graft Loss and Adverse Event eCRFs should be completed, and an SAE report of graft loss submitted. Dialysis treatments should be recorded on the Dialysis eCRF. Retransplantation should be recorded on the Surgical and Medical Procedures eCRF.

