6.2.3 Statistical model, assumptions and hypotheses

Graft loss, death, graft loss or death and antibody-treated biopsy proven acute rejections will be analyzed in a similar way to the tBPAR and time to tBPAR, although without the non-inferiority test. Other efficacy variables displayed in Table 6-1 will be presented within frequency tables to show the proportion of events and the CFZ533 treatment arm event rate will be compared with the control arm event rate using Z-statistics based on two-sided confidence intervals for differences in event rates.

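### The plan does not settle whether graft losses and deaths after a treatment stop or switch count in the Month 6 and 12 rates; read by reference, Protocol 9.5.1 leaves them out

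*Protocol*

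**What the plan says.** Protocol 9.5.1 lists the other efficacy variables under a single lead-in sentence: "Other efficacy variables will be analyzed similarly to the primary efficacy endpoint, although without the non-inferiority test". The list contains graft loss, death, and "Graft loss or death at Months 6 and 12", alongside tBPAR and BPAR. The section also plans simple event proportions with Z-based two-sided 95% intervals for the difference between arms.

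The analysis being borrowed is in Protocol 9.4.2. Under its heading on missing values and discontinuations it says: "The primary analysis only considers the events “on treatment", applying a window defined in 9.4.1 (redacted), "thus accounting for discontinuations from the randomized treatment arm or study". The binomial model in the same section takes the number of patients in the group as its denominator.

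Two rules in Protocol 5.5.5 link stopping treatment to these outcomes. Patients with steroid-resistant, vascular or Banff 2B-or-higher rejection "should be discontinued from study treatment, converted to local SoC and may be treated with other anti-rejection therapies". And: "If a subject is placed on permanent dialysis (or retransplanted), study treatment must be discontinued".

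SAP 6.2.3 says: "Graft loss, death, graft loss or death and antibody-treated biopsy proven acute rejections will be analyzed in a similar way to the tBPAR". The sentence goes on to add time to tBPAR as a second model to follow. In SAP 6.1.4, the Kaplan-Meier analysis censors event-free patients at last contact at or before the cut-off. The supportive Poisson model uses an exposure term described as "being the total follow up time in group i (times censored at treatment switch or discontinuation".

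**The concern.** Graft and patient survival show whether a CNI-free regimen has harmed patients. For such outcomes an on-treatment restriction is not a neutral way to handle discontinuation. Patients taken off study treatment for severe rejection are plausibly those most likely to lose the graft later. If that later loss is not counted, the exclusion is related to the outcome being measured.

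The binomial denominator makes this worse. A patient whose event is dropped is not censored; the patient remains in the group total as event-free. An arm with more severe-rejection exits could therefore look better on graft loss and death than it was.

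There is also a reproducibility problem. Two analysts following the same documents could produce different between-arm graft-loss and death rates from the same data. SAP 6.1.4 records that some patients had already been switched from randomised treatment, so the case is not hypothetical.

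**Working it through.** The documents give no expected rate, power or decision rule for graft loss or death, so there is no planned figure to reproduce. The check compares the counting rules, then asks how far a few events can move the result.

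**1. Which rule applies where**

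| Place | Counts events after a stop or switch? |
|---|---|
| Protocol 9.4.2, primary binomial analysis | No, beyond the redacted window |
| Protocol 9.5.1, graft loss and death | No, if 9.4.2 carries over by reference; only the non-inferiority test is excepted |
| Protocol 9.5.1, simple proportions | Not stated |
| Protocol 9.5.3, safety analyses | Yes, unless otherwise specified |
| SAP 6.1.3, binomial analysis | Not stated |
| SAP 6.1.4, Kaplan-Meier | Yes; censoring is at last contact or cut-off |
| SAP 6.1.4, supportive Poisson | No; time is censored at switch or discontinuation |
| SAP 6.2.2, descriptive rates | No limit stated |

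The all-data rule in Protocol 9.5.3 does not clearly reach the 9.5.1 comparisons, because the Protocol classes graft loss and death as efficacy assessments (6.5.1) and analyses them under the efficacy heading. SAP 6.2.3 points to both tBPAR and time to tBPAR, so it inherits rules that disagree.

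**2. Are the events collected?** Yes, in principle. Protocol 3.1.2, 5.5.10 and Section 6 keep Part 2 patients in follow-up to Month 12 whether or not they remain on treatment.

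**3. Sensitivity of the result.** Planned sizes (Protocol 3.1.4): 30 CFZ533, 15 control. One CFZ533 event is 1/30 = 3.3 points; one control event is 1/15 = 6.7 points. The counts below are assumed, for illustration only.

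- Raw difference = r1/30 - r0/15.
- 95% half-width = 1.96 × sqrt[p1(1-p1)/30 + p0(1-p0)/15].
- Posterior mean difference = (1/3 + r1)/(2/3 + 30) - (1 + r0)/(14 + 15), using the plan's Beta(1/3,1/3) and Beta(1,13) priors for tBPAR.

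| CFZ533 events counted | Control | Raw difference (points) | 95% half-width (points) | Posterior mean difference |
|---|---|---|---|---|
| 3/30 = 10.0% (all) | 1/15 = 6.7% | +3.3 | 16.6 | 3.333/30.667 - 2/29 = +0.040 |
| 2/30 = 6.7% (one dropped) | 6.7% | 0.0 | 15.5 | 2.333/30.667 - 2/29 = +0.007 |
| 1/30 = 3.3% (two dropped) | 6.7% | -3.3 | 14.2 | 1.333/30.667 - 2/29 = -0.025 |

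The rule applies to both arms. If instead the one control event were dropped, the raw difference would be 3/30 - 0/15 = +10.0 points. The direction of any distortion therefore depends on where the post-stop events fall.

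**The case against.** The strongest reply is that neither document states an on-treatment limit for graft loss or death; the inference rests on one word in 9.5.1. Protocol 9.4.3 uses firmer language when it applies the Month 3 method to later tBPAR and BPAR, and the reference in 9.5.1 to the non-inferiority test suggests that it has the statistical model in mind. Elsewhere the Protocol says so when it wants a treatment-status limit, as for eGFR in 9.5.3.1 and BK viremia in 9.5.3.2. The SAP definitions of graft loss and death (6.2.1) carry no treatment-status condition, nor does the ranked composite in SAP 7.1.2. SAP 6.1.4 also says that, because of switching, future interim analyses will place more focus on the Kaplan-Meier analysis, which keeps post-switch events.

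Much of this stands. A reader might infer that these events are certain to leave every Month 6 and 12 rate. The documents do not support that: the redacted window may retain events soon after a stop, the simple proportions have no stated rule, and the Kaplan-Meier analysis would include later events. Nor would the events vanish from the report. Both outcomes are handled through serious adverse event reporting, and safety analyses use all data.

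A graft loss that itself causes the stop probably counts, since Protocol 6.5.1 dates it to the start of permanent dialysis. A later death in the same patient is then already covered by the composite, so only death analysed alone is exposed by that route.

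What the reply does not supply is a counting rule for the between-arm comparison. It shows that the SAP can be read the other way, which is the inconsistency.

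**Conclusion.** The point holds as an unresolved counting rule. Protocol 9.5.1 by reference implies exclusion of graft losses and deaths after a stop or switch; the SAP's time-to-event analysis implies inclusion; its Poisson model implies exclusion; and its binomial section is silent. If the Protocol reading is followed, the exclusion is likely to be related to outcome, because severe rejection is itself a reason for leaving study treatment.

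The size of any bias cannot be computed: the documents give no switch counts, no expected graft-loss or death rates for this trial, and no visible window. A reader might also infer that CFZ533 would necessarily be flattered. That is plausible if severe-rejection exits are concentrated in that arm, but the documents do not establish it.

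The illustration shows only that one dropped CFZ533 event can remove a 3.3-point difference and two can reverse it, within intervals roughly 14 to 17 points wide on each side. No go/no-go rule is stated for these endpoints, and the Month 3 tBPAR decision is not affected. This should be corrected, but it does not undermine the trial's main conclusion.

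**What to change.** In Protocol 9.5.1 and SAP 6.2.3, state that graft loss, death, and graft loss or death count every event up to Month 6 and Month 12 in all Full Analysis Set patients, regardless of discontinuation or switch. Align SAP 6.1.4 so that any model reused for these outcomes does not censor at switch in the main version. Keep on-treatment counting as a labelled supportive analysis.

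The cost is about one sentence in each document and no new visits, since off-treatment follow-up to Month 12 is already required. There are two limits. Some counted events will have occurred on standard of care after a switch, so the comparison describes the assigned strategy including what followed it. And Protocol 6.5.1 records graft loss as a reason for study discontinuation, so deaths after graft loss may be less completely captured; the composite is unaffected.
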